COVER PAGE

Date/Version: November 11, 2016 / 1.2

Title of Protocol: The effect of MINGO (rice, mongo, moringa) as a nutritional supplement in patients with X-Linked Dystonia Parkinsonism (XDP) in Capiz, Philippines

Protocol Number: NCT03019458 Principal Investigator: [name].

Co-Investigators: None

Study Staff: MDSP members in the Philippines; Other healthcare providers and office staff, Sunshine

Care Foundation staff and community advocates (CAs)

Version 1.2 November 11, 2016

A linear mixed effects model will be used to determine if Mingo supplementation on top of regular diet would increase the BMI of XDP patients compared to regular diet alone. Baseline BMI, BFM scores, Eat 10 scores, and MGH SST scores, as fixed and random effects, will be incorporated into the model to adjust for their potential confounding effects. Data will be encoded in MS Excel 2007 and analyzed in R version 3.4.1, and using RStudio IDE, Version 1.0.153. All data will be analyzed by intention to treat.

Since this is a rare disease with a predefined number of 50, the study plans to have an acceptable power of 80% with the given limitation of 24 for the MINGO arm and 26 for the Control at the alpha level = 0.05. To achieve this power, we need to show an effect size of 2.23. The USCF Clinical and Translational Science Institute sample size calculator was used to find the effect size.

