People with XDP have, at present, an incurable disease that often causes significant movement abnormalities such that men with XDP are prevented from returning to work. Thus, men with XDP typically use social assistance given their unemployment. Medical care through the XDP Clinic is provided free-of-charge (through the support of the Sunshine Foundation) to people diagnosed with XDP by a neurologist with movement disorder training. Verbally, and in the written consent form, we will clearly state that people with XDP can decline research participation and still receive medical care through the XDP Clinic. Medical care for people with XDP is NOT contingent on participation in research.

Study Procedures

a. Assessing Baseline Metabolic Parameters

Once informed consent has been obtained, enrolled patients will be tested for the following metabolic parameters: uric acid, BUN, creatinine, potassium, and, exclusively for diabetic patients, A1C. These tests will require at most 5mL of blood from patients. These values will be collected before the three-month period of MINGO consumption by the trial group to satisfy the lab value exclusion criteria.

b. Patient Randomization

Placement into the trial or control group will be randomly assigned. The trial group will receive and consume MINGO throughout the duration of the study while the control group will not. Both groups will undergo the same number of study visits, with the same data information collected.

c. Trial Group MINGO Consumption: Training and Requirements

The researchers will organize a training session before beginning the trial where study staff, namely the community advocates (CAs), will be trained on the correct preparation of MINGO, how many sachets are required of patients, how to prepare food logs, and how and when measurements will be taken. The study staff will then teach the patients and caregivers belonging to the trial group this information in their homes.

MINGO sachets can be consumed mixed with other food and liquid items and will not be used to replace regular meals. Caregivers will ensure intake of MINGO by the patient and study staff will collect the empty sachet bags every two weeks, as well as review food logs to ensure that MINGO is being consumed properly. Any report of non-compliance will be logged and participants will be withdrawn from the study once they are found to have missed more than six MINGO sachets per week.

d. Patient Data Collection Procedures

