Each CA will be assigned a number of patients enrolled in the study. They will measure the weight of their group of patients for the entire duration of the study using a calibrated weight scale. The scale will be calibrated before every use (i.e. every two weeks). Each CA throughout the duration of the study will use the same scale. The CA will take weight measurements every two weeks at patient homes and a total of seven measurements will be done in three months.

Study staff will measure MUAC at the start of the study. MUAC measurements will be taken before the study, every four weeks, and at the end of the study.

At the end of the trial, the researchers may do multiple chart reviews in order to gather information on the patient's disease severity, caregiving, and family information.

Study Visits and Parameters to be Measured

Information that may be collected from/about subjects is listed on the:

- Data Collection Sheets
 - GUID information sheet: 10 identifying data elements for generating a Global Unique Identifier (GUID)
 - Movement disorder rating scales results from patient medical records
 - Burke-Fahn-Marsden Dystonia Scale (BFMDS)

- Unified Parkinson’s Disease Rating Scale (UPDRS)
 - XDP-MDSP Rating Scale
 - Swallowing assessments from patient medical records
 - MGH-SST
 - EAT-10
 - Caregiving scale and family information from patient medical records
 - Family APGAR
 - Modified Caregiver Strain Index (MCSI)
 - WHO-5 Index of Well being (WHO-5)
 - Trial participant sheet
 - Weight
 - Weight history
 - MUAC
 - Metabolic lab results
 - Demographic information from patient medical records
 - Patient education
 - Average annual income
- Food logs from caregivers and patients

Procedures

Phlebotomy

5 mL of blood from vein puncture may be used to obtain metabolic parameters on all subjects. The blood will be drawn by a professional trained in phlebotomy and will not be handled or collected by any of the study staff. A local lab that provides blood analysis for clinical use will be consulted.

Data Processing and Storage

Clinical data sheets will be labeled with the subject’s full name. At data entry, clinical data sheets will be checked for accuracy and completion. The subject’s Global Unique Identifier (GUID) will be generated. The GUID will be recorded on a code key corresponding to the subject’s name. No one at NeuroBANK™ will ever have access to the code key.

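### The SAP's only efficacy model puts its random effects on four confounders and names no patient effect, so the MINGO standard error is not reliably protected against repeated weights

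*SAP*

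**What the plan says.** The SAP (Version 1.2, analysis paragraph) gives one efficacy analysis: "A linear mixed effects model will be used to determine if Mingo supplementation on top of regular diet would increase the BMI of XDP patients", against regular diet alone. One sentence describes its random part: "Baseline BMI, BFM scores, Eat 10 scores, and MGH SST scores, as fixed and random effects, will be incorporated into the model". The stated purpose is adjustment for potential confounding. No patient term, grouping factor, visit term, covariance structure or formula is given. On handling and software it says "Data will be encoded in MS Excel 2007 and analyzed in R version 3.4.1", with nothing on rounding or scaling.

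The data are repeated measures. Protocol, Study Procedures, d: "The CA will take weight measurements every two weeks at patient homes and a total of seven measurements will be done in three months". Section b applies this to both arms: "Both groups will undergo the same number of study visits, with the same data information collected". The SAP's power paragraph takes patients as the independent units: "the given limitation of 24 for the MINGO arm and 26 for the Control at the alpha level = 0.05".

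For the covariates, the Protocol (Study Visits and Parameters to be Measured) lists "Swallowing assessments from patient medical records", meaning MGH-SST and EAT-10, and takes the dystonia scale from the same source. No repeat assessment is scheduled. Section d adds: "At the end of the trial, the researchers may do multiple chart reviews in order to gather information", including on disease severity. No rule fixes which dated score enters the model.

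**The concern.** Arm is a between-patient factor. Its standard error is valid only if the model recognises that six or seven BMI values from one patient are not independent, and a patient-level random effect is the usual device. The SAP assigns the random part to confounding instead. That job belongs to the fixed effects, and making the same covariates random as well adds nothing to it.

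The sentence can be coded in several ways:

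- **Covariate slopes by patient.** A covariate that is constant within a patient makes this a patient intercept in disguise, with a variance that depends on the size of the score. Raw values, or an added intercept, make it work nearly as intended. Standardised values with no intercept do not, because patients near the mean get almost no patient variance.
- **The four variables as grouping factors.** This separates patients only if their values are unique.
- **Covariate effects with no patient grouping.** Rows are then treated as independent.

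This is the only efficacy test in the SAP. A standard error that is too small would overstate the evidence for MINGO.

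**Working it through.** **1. The plan's own figure.** The inputs are 24 v 26 patients, 80% power and alpha 0.05 (SAP). The two-sided normal approximation gives a standardised difference of (1.96 + 0.842) x sqrt(1/24 + 1/26) = 2.802 x 0.283 = 0.793; the t calculation gives 0.809. One-sided values are 0.704 and 0.714. The SAP's 2.23 therefore cannot be in SD units, where power would exceed 99.99%. If it is in kg/m2, the implied SD is 2.23/0.809 = 2.76 (two-sided t), and up to 2.23/0.704 = 3.17 (one-sided normal). The SAP states no unit, SD or sidedness, so 2.23 can be neither confirmed nor called wrong. The SD enters only step 4.

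**2. No patient grouping, closed form.** With m rows per patient and within-patient correlation ICC (assumed), reported SE / true SE = 1/sqrt(1 + (m - 1) x ICC), and type I error = 2 x (1 - Phi(1.96 x ratio)). If the first weight is the baseline covariate, m = 6.

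- ICC 0.3: 1/sqrt(2.5) = 0.63, type I error 22%
- ICC 0.5: 1/sqrt(3.5) = 0.53, 29%
- ICC 0.8: 1/sqrt(5) = 0.45, 38%

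With m = 7, ICC 0.3 and 0.5 give 0.60 and 0.50 (24% and 33%).

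**3. Simulation of the codings.** REML, 24 v 26 patients, six visits, no treatment effect, the four covariates always kept as fixed effects and only the random part changed. There were 200 trials per cell, tested on 44 degrees of freedom. The Monte Carlo SE is about 1.5 points near 5% and 3 to 3.5 points above 25%. ICC and score distributions are assumed. Cells show SE ratio and type I error.

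| Random part | ICC 0.3 | ICC 0.5 | ICC 0.8 |
|---|---|---|---|
| Patient intercept | 0.94, 5.5% | 0.94, 6.5% | 0.92, 8.5% |
| BMI to 0.01 and scores as groups | 0.87, 9.5% | 0.84, 11.5% | 0.83, 11.5% |
| Raw slopes by patient, no intercept | 0.89, 8.0% | 0.86, 11.0% | 0.83, 10.5% |
| Centred slopes by patient, with intercept | 0.85, 10.0% | 0.86, 9.5% | 0.84, 10.0% |
| BMI to 0.1 and scores as groups | 0.81, 13.0% | 0.80, 12.0% | 0.75, 15.5% |
| Centred slopes by patient, no intercept | 0.73, 17.0% | 0.69, 17.0% | 0.61, 25.0% |
| No patient grouping | 0.59, 26.5% | 0.49, 29.5% | 0.40, 41.5% |

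Further runs at ICC 0.5 and 0.9 gave 0.93-1.01 for a patient intercept. Unrounded grouping, raw slopes, or slopes with an intercept gave 0.83-0.95. BMI to 0.1 as a group, or standardised slopes without an intercept, gave 0.68-0.75 (16-18%).

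The BMI-to-0.1 result is sensitive to the assumed scores. In a set of 800 trials per setting at ICC 0.9, it was 27.0% with 12 distinct values per score and 19.4% with 30.

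**4. Why rounding matters.** The expected number of opposite-arm pairs tied on BMI rounded to 0.1 is 24 x 26 x 0.1/(2 x sqrt(pi) x SD). With SD 2.76 this is 62.4/9.78 = 6.4; with SD 3.17 it is 5.6. Rounding to 0.01 gives 0.64.

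Ignoring score-group variance, the model treats a tied pair as one unit. At ICC 0.9 and total variance 1, it gives that pair's difference a variance of 2 x 0.1/6 = 0.033. The whole comparison has (0.9 + 0.1/6) x (1/24 + 1/26) = 0.073. One such pair outweighs everyone else once ICC passes 0.80. In the BMI-to-0.01 runs at ICC 0.9 with 12 score values, type I error was 15.7% with at least one such pair and 6.2% with none.

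**The case against.** The strongest reply is that the gap is smaller than it looks. An analyst fitting a mixed model must usually choose a grouping factor, and patient is the obvious choice. With raw slopes by patient, or any slopes plus a patient intercept, the test is only mildly anti-conservative. This stands. What remains is that the SAP lists its random effects by name, patient is not among them, and the choice is left to the analysis stage.

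The materially bad grouping case also needs steps that the SAP does not mention. The participant sheet lists weight, not BMI, so BMI is presumably calculated and need not be rounded. With assumed heights (mean 163 cm, SD 6.5) and BMI (mean 20, SD 2.76), opposite-arm ties average only 0.11 if weight is recorded to 0.1 kg and height to 1 cm, and 1.1 if weight is recorded to 1 kg. The other bad slope coding needs both standardising and leaving out the intercept. This stands too. A reader might infer that the trial faces a type I error approaching 30% from rounded BMI groups; the documents do not support that, because neither the rounding nor the grouping is stated.

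Nor is it stated that all four covariates are constant within a patient. That is true of baseline BMI by definition. For the three scores it is a strong inference from their source and the lack of a repeat schedule. If they did vary, the patient effect would still be missing.

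Finally, the SAP does not say that all seven weights enter the model. With one final BMI per patient the clustering problem would disappear, but a mixed model would then have no stated purpose.

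**Conclusion.** The concern holds, as something that should be fixed rather than as proof that the test is invalid. The named random effects do not do the job given to them and do not reliably do the job the design needs. Depending on coding, the MINGO standard error is:

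- slightly too small: ratio about 0.83-0.95, type I error about 6-13%;
- materially too small: about 0.7, 15-20%, if BMI is rounded and used as a group or standardised slopes are fitted without an intercept (individual settings fall outside this range);
- about 0.4-0.6, 22-42%, if patients are not grouped.

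These sizes rest on an assumed within-patient correlation, assumed score distributions and, for the tie counts, a BMI SD. The documents give none of these. The SD of 2.76 follows only if 2.23 is in kg/m2 and came from a two-sided t calculation. The dependence on coding does not need any particular value. A reader might infer that one of the larger figures is the trial's actual error rate; the SAP's wording does not determine which coding will be used, so it does not support that.

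**What to change.** - Drop the random role of baseline BMI, BFM, EAT-10 and MGH-SST and keep all four as fixed effects. Use score values dated before randomisation.
- Add a patient random intercept with small-sample degrees of freedom. If a week-12 or arm-by-time contrast is tested, add a patient time slope or use an unstructured within-patient covariance.
- Use weeks 2 to 12 as outcome rows, with baseline BMI as a covariate only.
- Name one target contrast. The choice matters: if the gain is linear, the average over weeks 2 to 12 is 7/12 = 0.58 of the week-12 effect, or 6/12 = 0.50 if week 0 is also an outcome row.

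The cost is SAP wording and reading score dates from the records; the weights are already scheduled in both arms. Some patients may have no dated score before randomisation. The interval may be slightly wider, but it will be valid.

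### The SAP's 80% power for an effect size of 2.23 does not describe the planned baseline-adjusted mixed model

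*SAP*

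**What the plan says.** The analysis paragraph of the SAP (Version 1.2) plans a linear mixed effects model to test whether MINGO added to the usual diet raises BMI, analysed by intention to treat. On covariates it says: "Baseline BMI, BFM scores, Eat 10 scores, and MGH SST scores, as fixed and random effects, will be incorporated into the model". The protocol (Study Procedures, d. Patient Data Collection Procedures) supplies the repeated data: weight is taken every two weeks, and "a total of seven measurements will be done in three months".

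The sample size paragraph of the SAP fixes the total at 50. It claims "an acceptable power of 80% with the given limitation of 24 for the MINGO arm and 26 for the Control", "at the alpha level = 0.05", and gives 2.23 as the effect size needed for that power. For the method it names a web tool and says only that its "sample size calculator was used to find the effect size". It does not state:

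- the unit of 2.23, or whether it is standardised;
- an SD or its source;
- whether the test is one- or two-sided;
- a correlation between visits, or the visit or average that the figure refers to;
- an allowance for attrition.

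**The concern.** The power statement and the planned model appear to concern different analyses. The stated power inputs are the arm sizes, alpha and 80%. Nothing reflects adjustment for baseline BMI or repeated weights, and these normally have a large effect on the precision of a BMI comparison.

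Because N was fixed in advance, the detectable difference is the only design information this paragraph conveys. Read as kg/m2, 2.23 would be a gain of 5.7, 6.1 or 6.4 kg at assumed heights of 1.60, 1.65 and 1.70 m (2.23 × height squared), in three months. A reader who takes that as the trial's sensitivity may judge a null result against the wrong yardstick.

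**Working it through.** **Inputs from the SAP:** 24 v 26, alpha 0.05, power 80%, effect size 2.23. **Assumed, because the documents are silent:** two-sided test (one-sided also shown), heights, correlations and 30% attrition.

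**1. Reproducing the SAP's figure.** The standard error of a difference between arms, in SD units, is sqrt(1/24 + 1/26) = 0.2831. By the noncentral t with 48 df, 80% power needs a standardised difference d = 0.809 two-sided (normal approximation (1.960 + 0.842) × 0.2831 = 0.793), or 0.714 one-sided.

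- *Standardised reading.* With d = 2.23 the noncentrality is 2.23/0.2831 = 7.88, and power exceeds 99.99%. The stated 80% is not reproduced.
- *Raw BMI reading.* 80% is reproduced only if the SD is 2.23/0.809 = 2.76 kg/m2 (2.81 by normal approximation), or 2.23/0.714 = 3.12 one-sided.

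**2. Can 2.76 be the SD that matters in the planned model?** In a baseline-adjusted comparison, the relevant SD is that of follow-up BMI among patients with the same baseline BMI. An SD of 2.76 would put 95% of such patients within ±1.96 × 2.76 × 1.65² ≈ ±15 kg of each other's expected weight after three months, at 1.65 m. That is not credible. A change-score SD of 2.76 would imply the same spread; if 2.76 were also the between-patient SD, it would need a baseline-to-follow-up correlation of only 0.5, since SD(change) = SD × sqrt(2(1 − r)). As a between-patient SD of BMI, 2.76 is unremarkable.

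**3. What adjustment would do, if 2.76 is the between-patient SD.** For one final visit adjusted for baseline, the residual SD is 2.755 × sqrt(1 − r²). The 80%-power multiplier is 0.810 for 24 v 26 (47 df) and 0.977 for 17 v 18, about 30% loss (32 df).

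| Assumed r | Residual SD | Detectable, 24 v 26 | 2.23 ÷ that | Detectable, 17 v 18 |
|---|---|---|---|---|
| 0.50 | 2.39 | 1.93 | 1.15 | 2.33 |
| 0.80 | 1.65 | 1.34 | 1.67 | 1.62 |
| 0.90 | 1.20 | 0.97 | 2.29 | 1.17 |
| 0.95 | 0.86 | 0.70 | 3.20 | 0.84 |

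Differences are in kg/m2. With 30% loss, the adjusted figure stays below 2.23 when r is above about 0.56 and exceeds it below that.

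For a true difference of 1.0 kg/m2 at 24 v 26, an unadjusted test with SD 2.76 has 24% power. The single-visit adjusted test has 55%, 82% or 98% at r = 0.80, 0.90 or 0.95.

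**4. Using the repeated weights.** For the mean of six post-baseline values (taking one of the seven as baseline) under compound symmetry, the SD multiplier is sqrt((1 + 5r)/6 − r²). The ratio of 2.23 to the detectable difference is then 1.73, 2.27, 3.06 or 4.23 at r = 0.50, 0.80, 0.90 or 0.95. These figures also leave out the three clinical scores and the random effects, so neither set is an exact calculation for the SAP's model.

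**The case against.** Four arguments stand against pressing this further.

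- **The source of 2.23 is inferred.** A reader might conclude that it can only come from an unadjusted comparison of single BMI values. The SAP gives no SD, unit or formula, and arithmetically 2.23 fits any two-group contrast with an SD near 2.76, change scores included. The ±15 kg argument makes the unadjusted reading likely; it does not prove it. This objection stands.
- **No fixed factor of overstatement follows.** It is tempting to say that the SAP overstates the detectable difference by 1.7 to 3 times. That range needs correlations that neither document gives. The ratio runs from 1.15 to 3.20 for one visit and from 1.73 to 4.23 for a six-visit mean, across r = 0.5 to 0.95. This stands too.
- **Attrition works the other way.** The protocol withdraws participants for missed sachets and lets subjects remove their data, and the power statement allows for neither. With 30% loss and r = 0.5, the adjusted figure is 2.33, slightly above 2.23. At r of 0.80 or more the direction holds even with that loss, but those correlations are assumed.
- **The consequence is limited.** N was predefined, so the documents do not show enrolment depending on 2.23. If the figure is conservative, the trial is more sensitive than claimed. The estimate, confidence interval and p-value do not change, and the interval itself shows which gains are excluded. This lowers the severity.

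None of this rescues the sentence. A simple two-group calculation can serve as a conservative bound, but the SAP does not present it as one.

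**Conclusion.** The statement is wrong as written, with moderate severity. No credible reading ties 80% power, 24 v 26 and 2.23 to the planned baseline-adjusted mixed model. The standardised reading fails on arithmetic alone. The kg/m2 reading fails because the SD it needs (2.76 two-sided, 3.12 one-sided) is not a believable spread of three-month BMI given baseline; that step rests on clinical plausibility and an assumed height, not on data in the documents.

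The size of the discrepancy is conditional. It depends on a between-patient SD of 2.76, the correlation, the visit or average chosen, and attrition. The documents therefore do not support saying that the trial can detect only a 6 kg gain, or that its true sensitivity is any particular smaller figure.

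**What to change.** Replace the power sentence in the SAP with the detectable difference at 80% power for the planned mixed model, keeping the fixed 24 v 26. State:

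- the difference in kg/m2;
- the SD and where it comes from, ideally serial clinic or registry weights if these exist;
- whether the test is one- or two-sided;
- the visit or average that the figure refers to;
- a short table over a range of baseline-to-follow-up correlations, for example 0.50, 0.80, 0.90 and 0.95;
- an attrition row, for example 17 v 18.

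Do not present 2.23 as the trial's sensitivity. If it is kept as a conservative bound, label it so, with its unit, SD and method.

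The cost is one SAP paragraph and a short calculation. No more patients and no change to trial procedures are needed.

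### Does the SAP need to say which BMI effect its figure of 2.23 refers to, and whether alpha 0.05 is one- or two-sided?

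*SAP*

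**What the plan says.** The SAP (Version 1.2) has two working paragraphs. The first sets the question and the method: "A linear mixed effects model will be used to determine if Mingo supplementation on top of regular diet would increase the BMI". It adjusts for baseline BMI and three baseline clinical scores, and analyses by intention to treat. It lists no visit, time or arm-by-time term, and does not say which coefficient carries the conclusion.

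The second gives the power statement, under the "given limitation of 24 for the MINGO arm and 26 for the Control at the alpha level = 0.05". It continues: "To achieve this power, we need to show an effect size of 2.23". An online "sample size calculator was used to find the effect size"; its inputs are not reproduced.

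The Protocol, under Patient Data Collection Procedures, schedules fortnightly weighing: "a total of seven measurements will be done in three months". Its Specific Aims name BMI and mid-upper arm circumference without a time point or summary measure.

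**The concern.** Seven weights allow at least three treatment effects: the difference at the last visit, the average difference over follow-up, and the difference in slope. The documents select none of them explicitly. The question is worded in one direction ("would increase the BMI of XDP patients compared to regular diet alone") while the level is given only as "at the alpha level = 0.05", so a one-sided test is not excluded. The power figure does not help, since a bare 2.23 could belong to any of these effects.

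Two things would be at stake. The verdict on MINGO could depend on a choice made after the data are seen, which would inflate false claims of benefit. And the 80% power could not be tied to the test that is eventually run.

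**Working it through.** **Inputs.** From the SAP: 24 MINGO, 26 control, alpha 0.05, power 80%, effect 2.23. From the Protocol: seven fortnightly weights, taken here as weeks 0, 2, …, 12. Not in the documents and therefore assumed: the SD, the correlation between visits, the shape of the gain, and complete data.

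**1. Can 2.23 be reproduced?** The detectable standardised difference is d = (z for alpha + z for power) × √(1/26 + 1/24), and the square root is 0.2831.

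- Two-sided: 2.8016 × 0.2831 = 0.793; by noncentral t on 48 df, 0.809.
- One-sided: 2.4865 × 0.2831 = 0.704; by noncentral t, 0.714.

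As a standardised difference, 2.23 would give power above 99.9%, so it is not on that scale. As kg/m2, the SD that makes it fit is 2.23/0.809 = 2.76 (two-sided) or 2.23/0.714 = 3.12 (one-sided). Over an assumed SD of 2 to 4 (normal approximation), two-sided power for 2.23 runs from 97.6% to 50.4%. The figure can be neither confirmed nor refuted, but it has a natural reading: a raw BMI difference.

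**2. Does the choice of effect change what 2.23 means?** If the gain is linear, the mean of weeks 2 to 12 is week 7, and 7/12 = 0.583. A gain of 2.23 at week 12 is then an average of 2.23 × 0.583 = 1.30, and an average of 2.23 is 2.23/0.583 = 3.82 at week 12. The readings differ, but only under that trajectory.

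**3. How often would the three tests disagree?** The tests were simulated as ANCOVA on week 12, ANCOVA on the mean of weeks 2 to 12, and a t-test on per-patient slopes. All were two-sided with a linear gain, under equal or first-order autoregressive correlation, where r is the correlation between baseline and week 12.

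| r | Gain giving 80% adjusted power, kg/m2 | Not unanimous at that gain | Not unanimous at a gain of 2.23, SD 2.755 |
|---|---|---|---|
| 0.5 | 1.93 | 32% to 35% | 23% to 25% |
| 0.7 | 1.59 | 26% to 38% | 9% to 12% |
| 0.8 | 1.34 | 23% to 39% | 2% to 4% |
| 0.9 | 0.97 | 20% to 40% | 0.1% or less |

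The second column is 0.809 × √(1 − r²) × 2.755. Disagreement of 20% to 40% therefore belongs to true gains of about 1.0 to 1.9 kg/m2. At 2.23, adjusting for baseline lifts week-12 power to 89% or more, and the tests mostly agree.

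**4. False claims of benefit with no true effect.**

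- One chosen effect: 2.5% two-sided, 5% one-sided.
- Best of three, two-sided: 4.4% to 5.8%.
- Best of three, one-sided: 8.1% to 10.9%.

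A different variance model (random slopes plus residual error) gave 4.2% and 7.9% for the two best-of-three figures. Reaching 8% to 11% needs both choices, effect and sidedness, to be made after the fact and in the same direction.

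**The case for a change.** The case for amending is that two or three sentences would close the gap at no cost in patients or visits, and that a directional question with unstated sidedness invites doubt. At the gain that gives about 80% adjusted power, sidedness alone moves week-12 power from 79% to 87% and changes the verdict in about 8% of trials. The shape of the gain matters too. With a maximum effect of 0.5 BMI units and other assumed variances, the three tests disagreed in 24% of trials for a linear gain, 36% for an early plateau, 51% for a late gain and 55% for a transient one.

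It is true that the text settles neither point, and that verdicts can differ when the true gain is well below 2.23. A clearer sentence would be better practice. The rates, however, come from assumed variances and trajectories, and from stand-in tests rather than the SAP's mixed model with its four covariates. They show that disagreement is possible, not how often it would occur here.

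The SAP also leans one way. With baseline BMI as a covariate and no time or arm-by-time term, its literal model has one arm coefficient: the average post-baseline difference. That is not conclusive, since the SAP names no arm term either and its list may be incomplete. But a slope test needs a term that the SAP never mentions.

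**Conclusion.** The omission stands as a fact: no contrast, sidedness, unit or SD is stated. It does not call for a change to the plan. The outcome, the comparison and the model class are named. The figure 2.23 is consistent with a raw BMI difference at an SD of about 2.8 (3.1 one-sided). The usual two-sided test of whichever single contrast the analyst adopts keeps its error rate and gives a valid conclusion.

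At the planned effect, disagreement between the candidate tests is about 25% or less at r = 0.5 and about 4% or less from r = 0.8 upward, assuming a linear gain, complete data and SD 2.755. Selective choice among two-sided tests would bring false claims to about 4% to 6%. The larger 8% to 11% assumes a second opportunistic choice, and nothing in the documents suggests that either would be made. Adding the missing words would document a choice, not correct an error.
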